17.1.5 Immune Related Adverse Event

Treatment emergent irAEs will be summarized using the following variables:

- The overall summary of treatment emergent irAEs will include the following categories:
 - irAEs
 - Related irAEs
 - irAEs, grade ≥ 3
 - Related irAEs, grade ≥ 3
 - irAEs leading to permanent treatment discontinuation
 - Related irAEs leading to permanent treatment discontinuation
 - Serious irAEs
 - Related serious irAEs

- irAEs leading to death
- Related irAEs leading to death
- Incidence of irAEs by SOC and PT: displaying in separate columns the All irAEs / Related irAEs / Grade ≥ 3 irAEs / Related Grade ≥ 3 irAEs
- Incidence of irAEs by SOC and PT and worst grade
- Incidence of related irAEs by SOC and PT and worst grade
- Incidence of irAEs leading to permanent treatment discontinuation by SOC and PT
- Incidence of related irAEs leading to permanent treatment discontinuation by SOC and PT
- Incidence of irAEs leading to death
- Incidence of related irAEs leading to death

A listing containing all the PTs used to identify irAEs and a listing containing all the irAEs in the study will be generated as well. A separate listing of irAEs started or worsened after on-treatment period will also be provided

17.1.6 Subgroup Analysis of Adverse Events

A listing of immunogenicity data and TEAEs will be provided containing subject ID, cohort (if more than one included in CSR), age, gender, study treatment start and stop date, all dates with positive ADA result, all dates with positive nAb results, preferred term of TEAE, TEAE start date, stop date, CTCAE toxicity grade and flags for immune-related adverse event or infusion related reaction or reason for permanent treatment discontinuation, as well as ADA status group.

Only subjects which are pre-existing positive, transient treatment-emergent positive, or persistent treatment-emergent positive will be listed.

17.2 Deaths

All deaths will be tabulated and listed for the SAF subjects. The death table will include the following information:

- Number of subjects who died
 - Primary reason for death
 - Disease progression
 - Adverse event related to study treatment
 - Adverse event not related to study treatment
 - Other
 - Unknown
- Number of subjects who died within 30 days of the last study treatment administration

- Primary reason for death
 - Disease progression
 - Adverse event related to study treatment
 - Adverse event not related to study treatment
 - Other
 - Unknown
- Number of subjects who died within 60 days of the first study treatment administration
 - Primary reason for death
 - Disease progression
 - Adverse event related to study treatment
 - Adverse event not related to study treatment
 - Other
 - Unknown

The listing of deaths will be provided with all the relevant information such as death date and reason for death. The death data will be ascertained from the dedicated Report of Death eCRF form.

17.3 Clinical Laboratory Evaluation

Laboratory abnormalities are classified according to NCI-CTCAE toxicity grading version 4.03 or based on normal ranges collected from laboratories. The toxicity grading is only related to the lab values itself and does not respect the non-numeric information as described in the CTC grading definition. CTCAE gradable parameters and associated toxicities are listed in Table 13.

Table 13 CTCAE Gradable Parameters and Associated Toxicities

Panel	Parameter (test)	Low direction toxicity	High direction toxicity
Hematology	Hemoglobin (HB)	Anemia	hemoglobin increased
	Leukocytes	white blood cell decreased	
	Lymphocytes	lymphocyte count decreased	lymphocyte count increased
	Neutrophils/ absolute neutrophils count (ANC)	neutrophil count decreased	
	Platelet count (PLT)	platelet count decreased	
Chemistry	Albumin	Hypoalbuminemia	
	Alkaline phosphatase (ALP)		alkaline phosphatase increased
	Alanine aminotransferase (ALT)		ALT increased
	Amylase		serum amylase increased
	Aspartate aminotransferase (AST)		AST increased

	Bilirubin (total)		blood bilirubin increased
	Cholesterol		cholesterol high
	Creatinine		creatinine increased
	Creatinine clearance	chronic kidney disease	
	Creatine kinase (CPK)		CPK increased
	Potassium	Hypokalemia	hyperkalemia
	Sodium	Hyponatremia	hyponatremia
	Magnesium	Hypomagnesemia	hypermagnesemia
	Calcium	Hypocalcemia	hypercalcemia
	Glucose	Hypoglycemia	hyperglycemia
	Gamma glutamyl transferase (GGT)		GGT increased
	Lipase		lipase increased
	Phosphates	Hypophosphatemia	
	Triglycerides		hypertriglyceridemia
Coagulation	Prothrombin time INR		INR increased
	Activated Partial thromboplastin time (aPTT)		aPTT prolonged

Grade 1 and 2 hyperglycemia are based on fasting glucose, they will not be graded for this study because blood samples are taken from non-fasted subjects.

For calcium, CTCAE grading is based on corrected calcium and ionized calcium (CALCIO), if available. Corrected calcium is calculated from albumin and calcium as follows

$$\text{Corrected calcium (mg/dL)} = \text{Calcium (mg/dL)} - 0.8 [\text{Albumin (g/dL)} - 4], \text{ or}$$

$$\text{Corrected calcium (mmol/L)} = \text{Calcium (mmol/L)} + 0.02 (40 - \text{Serum albumin [g/L]}).$$

Chronic kidney disease will be graded based on estimated creatinine clearance rate (eCcr, ml/min), which is derived using Cockcroft-Gault formula:

$$eCcr = \frac{(140 - \text{Age}) \times \text{Weight(kg)} \times \text{Constant}}{\text{Serum Creatinine } (\mu\text{mol/L})}$$

where the constant is 1.23 for men and 1.04 for women.

The corrected eCcr is derived as:

$$\text{Corrected eCcr (ml/min/1.73m}^2) = eCcr \times 1.73 / \text{BSA}$$

where BSA (body surface area, m²) = ([baseline height (cm) × weight (kg)] / 3600)^{0.5}.

The following are non-CTCAE gradable parameters collected in this study, their abnormalities are assessed as low, high, normal based on the comparison of observed values with normal ranges.

- Hematology: hematocrit, red blood cell (RBC), reticulocytes, mean corpuscular hemoglobin (MCH), mean corpuscular volume (MCV), mean corpuscular hemoglobin concentration (MCHC).
- Serum Chemistry: chlorine, C-reactive protein, lactate dehydrogenase (LDH), total protein, total urea, uric acid.
- Hormone: adrenocorticotrophic hormone (ACTH), anti-nuclear antibody (ANA), anti-neutrophil cytoplasmic antibody (ANCA), rheumatoid factor (RF), free thyroxine (Free T4), thyroid-stimulating hormone (TSH).

Laboratory abnormalities will be summarized using the worst grade during the on-treatment period. For these parameters which are graded with two toxicities such as potassium (hypokalemia/hyperkalemia), the toxicities will be summarized separately. Low direction toxicity (eg. hypokalemia) grades at baseline and post-baseline will be set to 0 when the variables are derived for summarizing high direction toxicity (e.g. hyperkalemia), and vice versa.

The change and percent change from baseline will be derived for parameters with numeric results.

17.3.1 Hematology and Clinical Chemistry Parameters

CTCAE gradable parameters

The laboratory toxicities will be tabulated by the worst on-treatment CTCAE grade or the shift of CTCAE grade from baseline to worst grade during on-treatment period using descriptive statistics (count and percentage). The highest CTCAE grade during the on-treatment period is considered as the worst grade for the summary.

- The worst grade during the on-treatment period will be summarized considering only patients with post baseline laboratory samples: Laboratory tests by NCI-CTCAE grade (0, 1, 2, 3, 4, and missing).
- The shift table will summarize baseline CTCAE grade vs. the worst on-treatment CTCAE grade (grade = 0, 1, 2, 3, 4, missing).

Non-CTCAE gradable parameters

Hematology, chemistry, and hormone evaluations which can't be graded per CTCAE will be summarized as:

- Shift from baseline value (low, normal, high) to above normal during on-treatment period
- Shift from baseline value (low, normal, high) to below normal during on-treatment period

Quantitative data will also be examined for trends using descriptive statistics (n, missing, mean, SD, median, Q1, Q3, minimum, and maximum) of actual values, absolute changes and percent changes from baseline to each visit over time. This summarization will apply to hematology and chemistry parameters with numeric results assessed at baseline, post-baseline, discontinuation, end of treatment, and/or safety follow-up visits based on visit windows specified in [Section 11](#).

The listings (hematology, chemistry, and hormone) will include all the laboratory parameters as available in the database with the relevant information such as visit, assessment date, parameter, value, normal ranges etc. Listings will be sorted by subject identifier, group variable, parameter, assessment date or visit.

Liver function parameters

ALT, AST, ALP, and total bilirubin are used individually or together to assess possible drug induced liver toxicity. The ratios of test result over upper limit of normal (ULN) for individual test or combined tests will be calculated and classified for these parameters during the on-treatment period.

Summary of liver function tests will include the following categories. The number and percentage of subjects with each of the following during the on-treatment period will be summarized by cohort, if applicable:

- $AST \geq 3*ULN / \geq 5*ULN / \geq 10*ULN / \geq 20*ULN$.
- $ALT \geq 3*ULN / \geq 5*ULN / \geq 10*ULN / \geq 20*ULN$.
- $(ALT \text{ or } AST) \geq 3*ULN / \geq 5*ULN / \geq 10*ULN / \geq 20*ULN$
- Total bilirubin $\geq 2*ULN$
- Concurrent $ALT \geq 3*ULN$ and $TBILI \geq 2*ULN$
- Concurrent $AST \geq 3*ULN$ and $TBILI \geq 2*ULN$
- $(ALT \text{ or } AST) \geq 3*ULN$ concurrently with total bilirubin $\geq 2*ULN$.
- $(ALT \text{ or } AST) \geq 3*ULN$ concurrently with total bilirubin $\geq 2*ULN$ and $ALP > 2*ULN$.
- $(ALT \text{ or } AST) \geq 3*ULN$ concurrently with total bilirubin $\geq 2*ULN$ and $(ALP \leq 2*ULN \text{ or missing})$.

Concurrent measurements are those occurring on the same date.

Categories will be cumulative, i.e a subject with an elevation of $AST \geq 10*ULN$ will also appear in the categories $\geq 5*ULN$ and $\geq 3*ULN$. Liver function elevation and possible Hy's Law cases will be summarized using frequency and percentage by cohort.

An evaluation of Drug-Induced Serious Hepatotoxicity (eDISH) plot will also be created to graphically display

- peak serum ALT(/ULN) vs. peak total bilirubin (/ULN) including reference lines at $ALT \geq 3*ULN$ and total bilirubin $\geq 2*ULN$.
- peak serum AST(/ULN) vs. peak total bilirubin (/ULN).

Listing of subjects with $ALT \text{ or } AST \geq 3*ULN$ or total bilirubin $\geq 2*ULN$ will include variables subject identifier, visit, date of collection, study day, parameter (ALT, AST, ALP, total bilirubin), result, unit, result/ULN, CTCAE grade.

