7.1.2.2 Expansion Phase

During the treatment period, the following assessments will be performed (see Appendix I for the detailed schedule):

- AEs and concomitant medications will be documented in each study visit.
- ECOG performance status will be assessed prior to trial treatment at Day 1 (unless the screening ECOG was performed within 3 days prior to Day 1) and every 2 weeks thereafter.
- Physical examinations will be performed prior to trial treatment in each visit until Week 13 (except Day 2 and Day 3), and every 6 weeks thereafter.
- Vital signs and body weight will be assessed prior to trial treatment in each visit until Week 13 (except Day 2 and Day 3), and every 2 weeks thereafter.
- The 12-lead ECGs (assessed prior to infusion and 2 hours \pm 20 minutes after infusion) will be assessed every 2 weeks until Visit 13, and every 6 weeks thereafter.
- The laboratory hematology and hemostaseology tests will be assessed prior to trial treatment and every 2 weeks thereafter.

- Full serum chemistry will be assessed prior to trial treatment, at Week 7 and Week 13 and then every 6 weeks thereafter. Core serum chemistry will be performed at Week 3, Week 5, Week 9 and Week 11 and every 2 weeks thereafter; if a full and core chemistry are scheduled at the same visit only the full chemistry will be performed. In addition, for subjects with liver metastases at baseline, samples for ALT, AST, total bilirubin, and alkaline phosphatase determination will be collected at Weeks 2, 4, and 6. Full urinalysis will be performed at screening and a basic urinalysis will be performed prior to trial treatment as defined in [Appendix I](#) (except for subjects with urothelial cancers, whose urine is usually unfit for analytical purposes).
- The urine β -HCG pregnancy test will be performed every 4 weeks in premenopausal women (before administration of the study drug).
- The tumor evaluation (see Section 7.3) will be performed at Week 7, and then once every 6 weeks for the first 12 months then every 12 weeks thereafter, with a tumor assessment visiting time window of 5 days prior to dosing.

Melanoma and mesothelioma: For subjects in the melanoma and mesothelioma cohorts only, fresh biopsies may be obtained on Day 43. These biopsies are optional.

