Tumor tissue (biopsy or archived surgical specimen); HPV determination for subjects in HNSCC cohort only (16)	X																				

AE: adverse events; ADA: anti-drug antibody (ADA); β-HCG: β-human chorionic gonadotropin; CA-125: cancer antigen 125; CT: computer tomography; CRPC: castrate-resistant prostate cancer; DLT: dose-limiting toxicity; ECG: electrocardiogram; ECOG: Eastern Cooperative Oncology Group; GEJ: Gastro-esophageal junction; HBV: hepatitis B virus; HCV: hepatitis C virus; HIV: human immunodeficiency virus; HNSCC: head and neck squamous cell carcinoma; HPV: human papilloma virus; IMP: investigational medicinal product; MRI: magnetic resonance imaging; PK: pharmacokinetics; SAE: serious adverse event; TSH: thyroid-stimulating hormone, T4: Free thyroxine.

\$ There is a 28-day washout / recovery period for prior anticancer treatment (e.g., cytoreductive therapy, radiotherapy [with the exception of palliative bone directed radiotherapy], immune therapy, or cytokine therapy except for erythropoietin) and major surgery before the start of trial treatment (Section 5.3.2). The screening procedures and baseline assessments will be completed within 18 days before trial treatment starts.

Following approval of Protocol Amendment 9, the visits at Weeks 2, 4, and 6 (Visit 4/Day 8, Visit 6/Day 22 and Visit 8/Day 36) have been restored for subjects with liver metastases at baseline for the collection of blood samples for ALT, AST, total bilirubin, and alkaline phosphatase determination.

* PK and ADA sampling on Days 2 and 3 are optional and only applicable for subjects in the secondary CRC and CRPC cohorts (expanded PK sampling) and the efficacy expansion cohorts (ADA sampling). Therefore, the visit at Day 2 is optional; however should a subject attend, blood draws for PK sampling and soluble factors (as applicable) are strongly encouraged.

A time window of up to 3 days before or 1 day after the scheduled visit day (-3/+1 days) will be permitted for all study procedures (except Days 2 and 3), except for body weight, which should be obtained on the same day as study drug administration. In addition, the tumor evaluation (see Section 7.3) has a tumor assessment visiting time window of 5 days prior to dosing (-5 days).

1. Tumor evaluation at the end-of-treatment visit should only be performed if no disease progression was documented previously.

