
Schedule of Visits
	
1. Screening/Baseline assessment (day -18 to first treatment)
 
2. Treatment phase
 
Visits will be conducted weekly until week 7 and every 2 weeks thereafter prior to the approval of Protocol Amendment 7. For subjects participating in the expanded PK sampling, visits at Days 2 and 3 will be required. Following the approval of Protocol Amendment 7, the visits at Week 2, 4, and 6 are no longer required and subjects will not be required to attend these visits.
 
3. Discontinuation visit and end-of-treatment visit
 
All subjects who discontinue study treatment prematurely for an AE should have a full safety evaluation at the time of discontinuation (discontinuation visit). For all subjects who have completed treatment, an end-of-treatment visit should be scheduled 4 weeks after the last administration of avelumab.
 
The end-of-treatment visit is scheduled 4 weeks after the last administration of avelumab but before any new therapy is started, if possible. The visit will comprise a full assessment of safety parameters, immunogenicity assessment, and tumor response assessment as appropriate.
 
4. Post-treatment follow-up (safety follow-up visit and survival follow-up)
 
All subjects will have a subsequent visit scheduled 10 weeks after the last administration of avelumab. The visit will include a full assessment of safety parameters.
 
AEs will be documented until the end of treatment visit. After the end of treatment visit only treatment related AEs have to be documented until the post-treatment safety follow-up visit. Subjects with a serious AE ongoing

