- There is no difference for visit windowing between tests from core serum chemistry panel and tests from full serum chemistry panel. Some subjects had non-core serum chemistry tests assessed at the scheduled visits only intended for core serum chemistry. Multiple protocol amendments are also taken into the consideration, as the full serum chemistry and hematology panels were assessed weekly until week 7 and bi-weekly thereafter prior to the approval of Protocol Amendment 7.
- For ECG assessment associated with study treatment dose, only assessments where time point (prior to infusion or 2 hr after infusion) are not missing will be considered for the analysis.

Table 5 Visit Window Definition for Safety Assessment

Assigned Study Day (Inclusive)		Planned Study Day (AWTARGET)	Analysis Visit (N) (AVISITN)	Analysis Visit (AVISIT)	Assessment
From (AWLO)	To (AWHI)				
~	1		1	Baseline	Lab, Vital Sign, ECG
1	1	1	2	Week 1 Day 1*	ECG
5	11	8	3	Week 2 Day 5-11	Lab, Vital Sign
12	18	15	4	Week 3 Day 12-18	Lab, Vital Sign
5	18	15	4	Week 3 Day 5-18	ECG
19	25	22	5	Week 4 Day 19-25	Lab, Vital Sign
19	25	22	5	Week 4 Day 19-25	ECG
26	32	29	6	Week 5 Day 26-32	Lab, Vital Sign
26	36	29	6	Week 5 Day 26-36	ECG
33	39	36	7	Week 6 Day 33-39	Lab, Vital Sign

40	50	43	8	Week 7 Day 40-50	Lab, Vital Sign
37	50	43	8	Week 7 Day 37-50	ECG
51	64	57	10	Week 9 Day 51-64	Lab, Vital Sign, ECG
65	78	71	12	Week 11 Day 65-78	Lab, Vital Sign, ECG
79	92	85	14	Week 13 Day 79-92	Lab, Vital Sign
79	106	85	14	Week 13 Day 79-106	ECG
93	106	99	16	Week 15 Day 93-106	Lab, Vital Sign
107	120	113	18	Week 17 Day 107-120	Lab, Vital Sign
121	134	127	20	Week 19 Day 121-134	Lab, Vital Sign
107	148	127	20	Week 19 Day 107-148	ECG
135	148	141	22	Week 21 Day 135-148	Lab, Vital Sign
149	162	155	24	Week 23 Day 149-162	Lab, Vital Sign
163	176	169	26	Week 25 Day 163-176	Lab, Vital Sign
149	190	169	26	Week 25 Day 149-190	ECG
177	190	183	28	Week 27 Day 177-190	Lab, Vital Sign
191	204	197	30	Week 29 Day 191-204	Lab, Vital Sign
205	218	211	32	Week 31 Day 205-218	Lab, Vital Sign
191	232	211	32	Week 31 Day 191-232	ECG

* only applies to 2 hr post dose, AWLO = Analysis Window Beginning Timepoint, AWHI = Analysis Window Ending Timepoint, AWTARGET = Analysis Window Target, AVISIT = Analysis Visit, AVISITN = Analysis Visit (N).

- Presentation of continuous and qualitative variables:

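### In the expansion SAP's by-visit liver-test tables, actual values at Weeks 2, 4 and 6 can differ from those at Weeks 3, 5 and 7 merely because different subjects are sampled

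*SAP*

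**What the plan says.** Expansion SAP 17.3.1 plans summaries by visit: "Quantitative data will also be examined for trends using descriptive statistics", covering actual values, absolute changes and percent changes, with n and the number missing. On scope, it states "This summarization will apply to hematology and chemistry parameters with numeric results", so ALT, AST, total bilirubin and ALP are included.

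The visits are the windows of SAP Section 11, Table 5. For laboratory data these include Week 2 (days 5 to 11), "Week 4 Day 19-25" and "Week 6 Day 33-39", interleaved with Weeks 3, 5 and 7. Unscheduled results also enter the windows. SAP Section 17 reports safety data by cohort, pooled, or both, with no split by liver metastasis.

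On who is sampled, SAP Section 11 says that the full chemistry and hematology panels "were assessed weekly until week 7 and bi-weekly thereafter prior to the approval of Protocol Amendment 7". SAP Section 6 (Schedule of Visits) says: "Following the approval of Protocol Amendment 7, the visits at Week 2, 4, and 6 are no longer required". The protocol goes one step further. In the Appendix I footnote to the expansion schedule, these visits "have been restored for subjects with liver metastases at baseline" following Amendment 9. Section 7.1.2.2 says that in those subjects "samples for ALT, AST, total bilirubin, and alkaline phosphatase determination will be collected at Weeks 2, 4, and 6". The SAP does not mention this step, although version 9.0 is dated 10 February 2017 and Amendment 9 is dated 22 December 2014.

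**The concern.** A table read for trends should follow much the same people from row to row. Here the Week 2, 4 and 6 rows have had three sampling rules: everyone before Amendment 7, nobody by schedule between Amendments 7 and 9, and only subjects with liver metastases from Amendment 9. The last rule selects on a factor that is plausibly related to the tests themselves. Where liver metastases go with higher liver tests, mean and median actual values would rise at even weeks and fall back at odd weeks with no change in any subject.

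The rows concerned cover the early treatment period. Protocol 3.4 reports two autoimmune hepatitis events with fatal outcome, and Protocol 3.7, drawing on ipilimumab experience, expects hepatic events at about 6 to 7 weeks. A reader should not have to guess whether an early movement in the actual values reflects the drug or the sampling rule.

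**Working it through.** The plan gives no figure to reproduce, so the check is whether the sampled set changes between rows, followed by an illustration of what that could do.

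**Who is scheduled at Weeks 2, 4 and 6 for the four tests**

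- Before Amendment 7 (30 July 2014, Protocol Appendix IV): all subjects.
- Amendment 7 to Amendment 9: none.
- From Amendment 9 (22 December 2014): baseline liver metastases only.
- Weeks 3, 5 and 7: all subjects throughout.

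The rules switch on approval, so the effective dates may be later than the amendment dates.

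**Which cohorts are exposed**

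SAP Section 9 places the urothelial efficacy cohort in Amendment 10 (4 March 2015), so all of it falls under the third rule. By contrast, Protocol 3.4 counts 184 NSCLC and 169 MBC subjects by 5 November 2014. Week 2, 4 and 6 values in the post-platinum NSCLC and MBC cohorts should therefore come largely from subjects sampled weekly before Amendment 7. The sampled set changes there too, but mostly not by liver metastasis.

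**Illustration, cohort wholly after Amendment 9**

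Let f be the share with liver metastases and d the difference in mean test (x ULN) between subjects with and without them. Neither is in the documents; both are assumed. With mean m in subjects without liver metastases:

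- even-week mean = m + d
- odd-week mean = m + f·d
- step = (1 − f)·d

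For the planned 200 urothelial subjects, the scheduled even-week n is 200f, against 200 at odd weeks, before dropout:

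| f | n at Weeks 2/4/6 | d = 0 | d = 0.25 | d = 0.5 | d = 1.0 |
|---|---|---|---|---|---|
| 0.20 | 40 | 0 | 0.200 | 0.400 | 0.800 |
| 0.35 | 70 | 0 | 0.163 | 0.325 | 0.650 |
| 0.50 | 100 | 0 | 0.125 | 0.250 | 0.500 |

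**Illustration, pooled over the 1640 planned subjects**

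Take 1640 − 480 = 1160 subjects as enrolled after Amendment 9, the 480 being those counted in Protocol 3.4. Let P be the number sampled weekly before Amendment 7, assumed to lie between 165 (the 90 NSCLC plus 75 MBC subjects in the July 2014 interim analysis, SAP Section 9) and 480.

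- even-week liver-metastasis share = f(P + 1160) / (P + 1160f)
- P = 165, f = 0.20: 265/397 = 67%
- P = 165, f = 0.50: 662.5/745 = 89%
- P = 480, f = 0.20: 328/712 = 46%
- P = 480, f = 0.50: 820/1060 = 77%

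The odd-week share is f itself, 20% to 50%. The step is (share − f)·d. At d = 0.5, over f = 0.20, 0.35 and 0.50, it is 0.13 to 0.23 x ULN.

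**Change from baseline**

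If no subject's value changes, each change is zero whoever is sampled. A simulated cohort of 150 with no drug effect shows the contrast. Its assumptions are f = 0.35, medians 1.3 and 0.8 x ULN, and log-scale SDs of 0.35 between and 0.1 within subjects. Mean actual values at Weeks 2 to 7 were 1.26, 1.01, 1.28, 1.02, 1.33 and 1.00 x ULN. Mean changes stayed between −0.03 and +0.04.

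One route could move the change rows. Protocol 7.4.3 has clinically significant abnormal results that were not present at baseline repeated weekly, and SAP Section 11 windows unscheduled results. Subjects without liver metastases who appear at even weeks may thus be selected for a new abnormality.

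**The case against.** The strongest reply is that liver safety is not judged from this table. SAP 17.3.1 also gives worst grade, shift from baseline, ALT and AST at 3, 5, 10 and 20 x ULN, concurrent bilirubin categories, possible Hy's Law cases, eDISH plots and a subject listing. These are not by-visit summaries, so they cannot alternate between weeks. This stands in full. A reader might infer that the hepatotoxicity assessment is compromised, and the documents do not support that.

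A reader might also infer that a real early rise could not be told from the sampling change. That goes too far: the same table prints within-subject change, n and missing. Still, a lower n does not say who remains, and the SAP does not say it elsewhere.

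Nor do the Week 2, 4 and 6 rows hold liver-metastasis subjects exclusively. Unscheduled repeats, delayed visits and pre-Amendment 7 data enter too. The restriction applies to scheduled visits.

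Finally, SAP Section 11 says the windowing considered multiple amendments, and Section 6 refers to the protocol schedule, which carries the Amendment 9 rule. But the only change the SAP describes for these visits is that of Amendment 7, and nothing in the table specification responds to the later rule. Protocol 8.5.1 makes these analyses exploratory, which limits the consequence without making the rows comparable.

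**Conclusion.** The point holds for the actual-value rows of ALT, AST, total bilirubin and ALP in the expansion by-visit tables. Even-week and odd-week rows can differ through sampling alone, most in cohorts opened after Amendment 9 and less in those largely enrolled earlier. Change-from-baseline rows need not alternate unless liver-metastasis subjects change differently or repeats for new abnormalities enter the windows.

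No size can be derived from the documents, which give neither the liver-metastasis share nor liver-test means by metastasis status. The steps shown are illustrations, and at d = 0 there is none. Expansion eligibility (AST and ALT up to 2.5 x ULN, bilirubin up to 1.5 x ULN, no ALP limit) restrains the baseline difference for three of the tests without removing it. No primary analysis or stopping rule is touched. It is a specific reporting defect worth correcting because the correction is cheap.

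**What to change.** In expansion SAP 17.3.1, present the by-visit summaries of the four tests separately by baseline liver metastasis (yes/no) at all visits, each stratum with its own baseline and n. Limit any all-subject trend row to visits scheduled for everyone: baseline, Weeks 3, 5, 7, 9 and onward. Keep the pre-Amendment 7 Week 2, 4 and 6 values in their stratum; removing those weeks for subjects without liver metastases would discard results collected by design. Keep all values in the listings and in the worst-grade and threshold tables. Update SAP Section 6 to the Amendment 9 visit schedule.

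The cost is SAP wording, one extra table split and smaller n per stratum. No new data are needed: the protocol already uses liver-metastasis status to assign these visits, and SAP 13.1 already uses it for the Bellmunt score in the urothelial cohorts.
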